9.6 Concomitant Treatment

The clinical study is concerned with no more than 2 lesions per patient. Within the study no additional concomitant treatment will be offered to the subjects outside the normal local clinical routines. At the recall appointments, normal recall procedures will be applied.

10 Data Management

10.1 Data Management Plan

10.1.1 Data collection

Data collection is done using the CRF that exists in the form of a paper version. The method is to employ paper CRFs to collect the data responses, which are subsequently translated to the monitoring database. These paper CRFs are filled up by the investigator according to the protocol.

10.1.2 CRF tracking

The entries made in the CRF will be monitored by the designated DMG clinical monitor for completeness and filled up CRFs are entered into the database. CRFs are tracked for missing pages and illegible data manually to assure that the data are not lost. In case of missing or illegible data, a clarification is obtained from the investigator and the issue is resolved.

10.1.3 Data validation

Data validation is the process of testing the validity of data in accordance with the protocol specifications. Discrepancy is defined as a data point that fails to pass a validation check. Discrepancy may be due to inconsistent data, missing data, range checks, and deviations from the protocol. Ongoing quality control of data processing is undertaken by the monitor at regular intervals during the course of clinical trial.

10.1.4 Discrepancy management/query resolution

Discrepancy management includes reviewing discrepancies, investigating the reason, and resolving them with documentary proof or declaring them as irresolvable. Discrepancy management helps in cleaning the data and gathers enough evidence for the deviations observed in data. For discrepancies that require clarifications from the investigator, the monitor will discuss the query with the investigator or will be sent to the site. The Investigators will write the resolution or explain the circumstances that led to the discrepancy in data.

10.2 Data Quality Assurance

Data Quality Assurance is a critical phase in clinical research, which leads to generation of high-quality, reliable, and statistically sound data from the clinical trial. The clinical monitor is actively

involved in all stages of clinical trial right from inception to completion. For Data Quality DMG has implemented an adequate process knowledge that helps to maintain the quality standards of data management processes. Various procedures in Clinical Data Management including Case Report Form (CRF) designing, CRF annotation, monitoring database designing, data-entry, data validation, discrepancy management are assessed by the monitor for quality at regular intervals during a trial.

10.3 Data Privacy Protection

Electronic study files will be password protected and reside on a computer that is also password protected. Paper records will be maintained in a locked cabinet in a space that has locked entryways.

10.4 Study Database

Electronic study files as well as paper records, such as CRFs, will be collected and checked for completeness by the clinical monitor during the continuous on-site visits.

A carbon copy of the paper records will be stored at sponsor site. Moreover study data will be transferred into a monitoring specific database.

11 Biostatistical Design

11.1 Prospective Design

Controlled, randomized, blinded study, single center design.

11.2 Determination of Sample Size

50, non-cavitated early caries lesions, or areas of demineralization, in proximal surfaces of primary molars will be enrolled in this study. Early caries lesions with demineralization seen on occlusal surfaces will be excluded from participation, along with white spot lesions from hypoplasia or fluorosis.

11.3 Evaluation Strategy

The bitewing radiographs will be examined and assessed by evaluators for positive, none or negative change in size and density.

11.4 Statistical Analysis

11.4.1 Descriptive Statistics

Descriptive statistics (means, standard deviations, counts, and percentages) will be calculated for all variables. A Chi-square test of association will be performed to evaluate if there is a significant difference in caries arrest by treatment group at a significance level of 0.05. Additional Chi-square tests of association will be performed to determine if there is a significant association with the secondary outcomes by treatment group.

11.4.2 **Blinding**

Each subject enrolled into this study will be assigned a unique identifying code number. Every effort will be made to maintain the confidentiality of each study subject's identity. No presentation or publication of the study data will identify any study subject.

11.4.3 **Evaluation of Records**

SFE laser optical device image diagnoses from each time point will be compared to diagnoses from radiograph and visual exams from chart review from the same visit.

- For radiograph and visual exams: Assessments of caries lesions per standard of care will be abstracted from the electronic dental record system (Axium) and recorded on CRF.
- For SFE laser optical device image: Recordings from the device will be used to assess caries lesions and recorded on CRF.

11.4.4 **Missing Data**

Missing data due to dropouts have been accounted for in adjusted sample size. The missing data will be at random. Data of dropouts will be assigned as "last observation carried forward".

11.4.5 **Statistical Software**

STATA Data Analysis and Statistical Software will be utilized to perform data analysis.

12 Method of Reporting

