6.2 Specific Aimes (Primary Endpoints)

6.2.1 Specific Aim I

- Caries arrest evaluated by bitewing radiographs

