The primary endpoint in this study is the proportion of study lesions that have progressed, whereby a difference in caries progression of 40% after 2 years between resin infiltrated teeth and control will be assumed. This difference is based on a previous infiltration study by Ekstrand et al. [45] who reported a 1-year difference in caries progression in primary teeth of 39% (resin infiltration (23%) vs. control (62%)), which was furthermore comparable to results obtained in young adults. Martignon et al [42] for example reported a difference in caries progression in permanent teeth of 37% and 38% after 1 and 2 years respectively; and Meyer-Lueckel et al. of 30% after 18 months.

Based on an assumed difference in caries progression of 40% between resin infiltrated teeth and control, with alfa = 0.05 and a power of 80% the calculated sample size (t-test; matched pairs) would be 42 lesions to find significant differences. To allow for a potentially attrition rate of at least 20% over a period of 2 years a total of 50 lesions will be included.

Statistical Analysis

All evaluations are performed by one trained examiner. The primary outcome is proportion of study lesions that progressed after 2 years as measured via dental examination and pairwise comparison of radiographs. Differences between groups will be tested using Fisher's exact test.

Secondary outcomes are the proportion of study lesions that progressed after 1 year as well as change in categorical lesion depth (progression to next depth category lesion; E1->E2->D1->D2->filling) after 1 and 2 years as measured by pairwise comparison of radiographs. In addition, the change in categorical lesion depth will be determined via SFE laser optical device imaging after 1 and 2 years and compared to the change in categorical lesion depth as measured by pairwise comparison of radiographs. Differences in categorical lesion depth will be analyzed with Chi-square tests with 95% confidence interval (95% CI) and P = .05.

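### Protocol 11.4.1 names a Chi-square test for the primary outcome and the SAP names Fisher's exact test; near the planned effect the two can give different answers in roughly 8–12% of trials

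*Combined protocol and SAP*

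**What the plan says.** Protocol section 6.2.1 lists this under the primary endpoints: "Caries arrest evaluated by bitewing radiographs". Section 11.4.1 gives the test: "A Chi-square test of association will be performed to evaluate if there is a significant difference in caries arrest by treatment group". The level set there is 0.05. The section does not mention a continuity correction, sidedness or a time point.

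The SAP, under Statistical Analysis, defines the outcome: "The primary outcome is proportion of study lesions that progressed after 2 years as measured via dental examination and pairwise comparison of radiographs". The next sentence reads: "Differences between groups will be tested using Fisher's exact test". The SAP uses Chi-square only for categorical lesion depth.

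The SAP's sample-size paragraph sets the level and power: "with alfa = 0.05 and a power of 80% the calculated sample size (t-test; matched pairs) would be 42 lesions". The effect is stated as "a difference in caries progression of 40% after 2 years between resin infiltrated teeth and control will be assumed". Its source is a one-year study in primary teeth with 23% progression after infiltration and 62% in controls. Fifty lesions are enrolled to allow for at least 20% attrition, and protocol section 9.3 assigns 25 to each arm.

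No visible text ranks the protocol and SAP. Protocol section 12.1 has the monitor check the analysis against the protocol, so the SAP cannot simply be assumed to prevail.

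**The concern.** If arrest means no progression, the two texts prescribe different tests for one primary comparison. With 20 to 25 lesions per arm the tests are not interchangeable: Fisher's exact test is conservative, and the uncorrected Chi-square sits near or a little above its nominal level. A borderline result could be called significant under one text and not under the other, and nothing fixes the choice before the data are seen. The stated 80% power comes from a third method, a matched-pairs t-test, so it describes neither named analysis.

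**Working it through.** **Inputs.** Level 0.05 (both texts), taken as two-sided because neither says. Difference 40 points (SAP). The SAP gives no arm rates for the 40-point case, so 62% vs 22% is assumed; 63/23, 60/20, 70/30 and the cited 62/23 are used as a range. Lesions per arm: 25 with no loss; 21 (half of 42); 20 after 20% loss (50 × 0.80 = 40). Lesions are treated as independent and arrest as the complement of progression.

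**The plan's 42 lesions.** For two independent proportions with unpooled variance, n per arm = (1.960 + 0.842)² × [p₁(1−p₁) + p₂(1−p₂)] / (p₁−p₂)².
- 63/23: 7.85 × (0.2331 + 0.1771) / 0.16 = 20.1, so 21 per arm, 42 in all.
- 62/22: 7.85 × (0.2356 + 0.1716) / 0.16 = 19.98, so 20 per arm, 40 in all.
- A paired t-test on binary differences at 62/22 with zero within-pair correlation gives 22 pairs, 44 lesions.

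So 42 can be reached, but only with rates or a correlation that the documents do not state, and not with either named test.

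**Comparison of the tests.** Every possible 2×2 table was enumerated and weighted by its binomial probability. At 62% vs 22%:

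| Lesions per arm | Chi-square power | Fisher's power | Tests disagree |
|---|---|---|---|
| 25 | 86.4% | 78.6% | 7.8% |
| 21 | 76.8% | 64.4% | 12.4% |
| 20 | 73.9% | 63.4% | 10.6% |

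At the cited 62% vs 23%, disagreement is 8.3%, 12.8% and 11.0%. Across all the rate pairs, Fisher's power is 76–79% at 25 per arm and 60–65% at 20 per arm.

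**Direction.** At these sizes no table is significant on Fisher's and not on Chi-square, so the reverse disagreement has probability 0.

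**Examples.** For 12/20 vs 5/20, X² = 40 × (12×15 − 8×5)² / (20×20×17×23) = 5.01, p = 0.025; Fisher's p = 0.054. For 14/25 vs 7/25, X² = 50 × (14×18 − 11×7)² / (25×25×21×29) = 4.02, p = 0.045; Fisher's p = 0.085.

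**No true effect.** The tests disagree in about 2–3% of trials. At 25 per arm, with a common rate of 20–60%, Chi-square rejects in 5.4–6.5% and Fisher's in 2.2–3.3%. The highest Chi-square rate is 5.6% at 21 per arm and 5.3% at 20.

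**Yates correction.** At 62/22 the corrected Chi-square disagrees with Fisher's in 0% of trials at 21 or 25 per arm and 3.1% at 20.

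**The case against.** Four objections have weight.

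- **The rate is conditional.** A reader might infer that one trial in ten would split whatever the truth. The figures do not support that: the rate needs a true effect near the plan's and an uncorrected Chi-square. Uncorrected is the natural reading of 11.4.1, but it is an assumption.
- **The number analysed may be nearer 25 per arm.** Section 11.4.4 carries dropouts' last observations forward, which points to the 8% figure. Table 14.1.2 is less clear: for lost contact and withdrawn consent it records a dropout without mentioning carry-forward. The range therefore stays open.
- **The error inflation is small.** A reader might infer that a free choice of test badly inflates false positives. It does not. All disagreement runs one way, so picking the significant test is the same as always using Chi-square, at most about 6.5% at 25 per arm and 5.3% at 20. This argues against the highest severity.
- **The endpoints are not worded alike.** The protocol speaks of arrest on bitewings; the SAP of progression at 2 years by examination and radiographs. Section 11.3 scores change three ways, so a 2×3 Chi-square is possible. That limits the arithmetic above, but it is a further reason to reconcile the texts.

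None of these removes the contradiction.

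**Conclusion.** The inconsistency is genuine and should be fixed. Near the planned effect it could change the primary yes/no result in about 8% of trials at 25 lesions per arm and 11–12% at 20–21, always towards significance under the protocol's test. With no effect, or with Yates correction, the tests rarely differ. The figures rest on two-sided testing, assumed arm rates, an uncorrected Chi-square, arrest as the complement of progression, and independent lesions.

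Independence is doubtful because section 6.4 allows two lesions per patient. Neither test handles within-patient correlation, so naming one does not settle that issue. A reader might also infer that the plan needs a different exact test or one stratified by baseline E1/E2 depth. The documents contain no such stratification, and another unstratified exact test would make the same independence assumption.

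The more practical consequence is for power: if Fisher's governs, the stated 80% is not met even with no loss.

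**What to change.** 1. Keep the SAP's Fisher's exact test as the single primary test of the proportion of lesions progressed at 2 years, and state that it is two-sided at 0.05.
2. In protocol 11.4.1, replace the Chi-square sentence for the primary outcome with the same test and the SAP's endpoint wording, saying how arrest relates to progression.
3. Rewrite the SAP's sample-size paragraph for that test, with the assumed arm rates: power about 76–79% at 25 per arm and 60–65% at 20 per arm for differences of 39–40 points. State that these figures assume independent lesions although up to two per patient are allowed.

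The cost is one sentence in the protocol, a few words in the SAP's test sentence and a rewritten sample-size paragraph. No data collection changes, but the sponsor must accept a stated power below 80% at the current size.

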5.1 Risk Analysis of the Medical Device

There is a minimal risk associated with the device itself and the procedures involved in its use, as identified by risk assessment and post-market experience of substantially equivalent materials, beyond the common risks related to standard dental treatment.

Definition: Minimal risk is the probability and magnitude of harm or discomfort anticipated in the research and not greater in and of themselves than those ordinarily encountered in daily life or during the performance of routine physical or psychological examinations or tests [45 CFR 46.102(i)]

The entire treatment in each aspect, including lesion size and location, all materials, equipment and techniques used, is part of regular daily life. Dentist visits, like in this study, resulting in caries detection, diagnosis and management by regular preventive regimen or sealant are not at all out of the ordinary. It is –alas- rather ubiquitous and a common part of daily oral health care provisions that our professions provides to the public. Therefore, the risk is NOT greater than routine dental practice. The care provided meets this definition of minimal risk.

The SFE technology has been used in multiple human applications safely and efficaciously. Therefore, there is low risk in use of the technology in the dental setting. The device was deemed to be a non-significant risk device by the FDA. If a child expresses dismay or stress during the SFE imaging process, the participant will be withdrawn from further study participation.

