7.2.1 Inclusion Criteria

Children ranging in age from 6-13 years will be eligible to participate. The patients must have a one early caries lesions present in primary molars. Up to 2 early caries lesions may be enrolled per patient, providing the second lesion is in a separate quadrant. All patients must be in good general health and free of any systemic disease or disability, preventing any unnecessary procedures. Patients must be available, as well as can be anticipated, for one-year, and two-year recalls.

Criteria used to assess teeth for acceptance into this study include: (1) teeth fully erupted, in functional occlusion and (2) radiographic evidence of early caries in interproximal areas (1 or 2, Ekstrand's criteria⁹). The patients will be appointed for a pre-study appointment after the legal guardian has undergone the informed consent process for the patients to take part in the study.

Selected teeth will be dried for at least 5 seconds with compressed air and study lesions examined under a standard operating light in the CPD clinic. Visual exam: Ekstrand's criteria⁹ will be used to evaluate and record (Table 8.4.2.1). Study lesions scored in categories 1 or 2 from Ekstrand's criteria will be enrolled in the study.

For radiograph examinations the DMG's criteria⁷ will be used to evaluate and record carious lesions. Study lesions scored in categories E1 and E2 from DMG's criteria⁷ will be enrolled in the study (Table 8.4.2.2 and Figure 3).

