8.2 Clinic visits

A trained study clinician will perform all standard clinical assessments of study lesions in groups 1 and 2, including visual exam and radiograph exam. The study clinician will provide Icon treatment to all study participants randomized to study arm 1 after the radiograph and visual exam. The study clinician will provide oral hygiene instruction and topical fluoridation therapy (Duraphat fluoride varnish) to all study participants randomized to study arm 2 after the radiograph and visual exam.

A trained study clinician will capture the SFE laser optical device image of the study lesions from all study participants. The study examiner will be trained and calibrated by the HPL research team prior to start of study. SFE laser optical device image diagnoses from baseline will be compared to diagnoses from radiograph and visual exams from chart review from the same visit.

Table 8.2 Overview of the procedures during each visit

Procedure	Screening visit	Baseline and Intervention	12 Month Follow-up	24 Month Follow-up
Time		D-0	M 12 (± 3 m)	M 24 (± 3 m)
Patient information	x			
Oral examination	x		x	x
Informed consent	x			
Medical history	x			
Inclusion and exclusion criteria	x		x	x
Selection of eligible lesions	x			
Caries risk assessment	x			
Placing ortho spacers(tx group) D-21 to -7 prior to BI		x	x	x
Randomization	x			
Radiographic examination		x	x	x
Examination by SFE Before spacers placed	(x)*	x		
Examination by SFE Before & After Icon placed		x	x	x
Examination by SFE		x		
Visual Assessment of lesion		x	x	x
Intervention (Infiltration) (EXPERIMENTAL)		x		
Instruction for oral health care		x	x	x
Record of adverse effects		x	x	x
Fluoridation (CONTROL)		x	x	x

*Can be done at screening or baseline appointment

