9.4 Intervention Visit

9.4.1 Intervention Site “TREATMENT”

All groups will undergo visualization of lesions with radiograph exam, visual exam, and SFE laser optical device exam. 2 weeks prior to the SFE laser optical device exam orthodontic rubber spacers will be inserted next to the study lesions to separate the proximal space for better visualization. The initial SFE exam will occur prior to tooth separation at this visit.

Prior to Icon placement, SFE laser optical device will be performed. The study clinician will provide Icon treatment to all early lesions randomized to study arm 1 after the radiograph and visual exam and a post SFE laser optical device will be performed. The test lesions will be treated using Icon (DMG, Hamburg, Germany) following the instruction for use.

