9.5 Follow-up Evaluations

Follow-up assessments will occur at months 12 and 24 from baseline +/- 3 months. Study patients will be reminded of their follow up visit. The following will occur at all follow-up visits:

- Two weeks prior to the appointment (-21 to -7 days) Orthodontic rubber spacers will be inserted next to the iconized lesions to separate the proximal space for better visualization.
- Radiograph exam of study lesion
- Visual exam of study lesion
- SFE laser optical device imaging of study lesion

Results are documented in CRF (Appendix A1).

If study lesions are noted to be progressing at any point the study clinician will refer the participant for standard-of-care treatment to the CPD Resident Clinic. Progression is defined as lesion changes

from E2 to D category according to DMG's criteria. The study participant will no longer participate in the study at this point.

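### By implication, the protocol's carry-forward rule counts a lesion lost before month 12 as not progressed; the SAP neither replaces the rule nor plans a sensitivity analysis

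*Combined protocol and SAP*

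**What the plan says.** Protocol section 11.4.4 states "Missing data due to dropouts have been accounted for in adjusted sample size. The missing data will be at random", and then "Data of dropouts will be assigned as 'last observation carried forward".

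The SAP makes the proportion of lesions progressed after 2 years the primary outcome, tested with Fisher's exact test. It mentions attrition only in the sample size, where 42 lesions become 50 to cover at least 20% loss. It states no missing-data rule, and neither document plans a missing-data sensitivity analysis.

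The schedule and entry rules matter here:
- Section 7.2.1 enrols "Study lesions scored in categories E1 and E2".
- Section 9.5 says "Follow-up assessments will occur at months 12 and 24 from baseline". In Table 8.2 the first visit column after baseline and intervention is "12 Month Follow-up".
- Section 9.5 also says "If study lesions are noted to be progressing at any point the study clinician will refer the participant", and ends that child's participation.

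Table 14.1.2 (section 14.2) treats losses in three ways:
- Progression to D2 or D3, or pulpitis, is scored as progressed and as a failure.
- Adverse reactions, children who cannot be examined and lesions treated by an external dentist are dropouts with carry-forward.
- Children who cannot be contacted or who withdraw are marked only as dropouts. Carry-forward reaches them through section 11.4.4 alone.

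Section 5.1 adds a further exit: "If a child expresses dismay or stress during the SFE imaging process, the participant will be withdrawn from further study participation".

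**The concern.** For an outcome that starts as not progressed in every lesion, carrying a baseline value forward records a success. The assumption that data are missing at random does not justify this, because even completely random early loss lowers the progression rate in each arm.

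Progression is then undercounted in whichever arm loses lesions early. Equal loss shrinks the Icon-control difference, which is conservative for Icon in the SAP's test for a difference. It is not conservative for Hypothesis I in section 4.2.1, which says that Icon performs similarly to control. Heavier early loss on control shrinks the difference further, and heavier early loss on Icon works in Icon's favour. With no sensitivity analysis, a reader of the results could not tell which had happened.

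The external-dentist row raises a related problem. A lesion last read as unprogressed and then treated elsewhere keeps that earlier score, while the SAP's secondary depth scale ends in a filling. The same lesion could sit at the top of one scale and count as unchanged on another.

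**Working it through.** **The plan's own figures.** With 23% vs 63%, unpooled variance, two-sided 0.05 and 80% power, (1.960 + 0.842)² × (0.23×0.77 + 0.63×0.37) / 0.40² = 20.1, so 21 per arm, or 42 lesions. The step to 50 matches 42 × 1.2 = 50.4. So 20% loss is the natural planning value.

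**Inputs.** 25 lesions per arm (section 9.3). Progression of 62% control and 24% Icon at 24 months, and 53% and 16% at 12 months, from a study cited in section 4.3.4, which the SAP identifies as being in permanent teeth. Lesions are treated as independent. The timing and arm split of loss are not in the documents, so ranges are shown. Fisher's test is two-sided at 0.05, by full enumeration.

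**Formula.** With loss L, and share e of it before month 12 (scored 0), the carried-forward rate is (1−L)·p24 + L·(1−e)·p12.

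**Equal 20% loss.** With no loss the difference is 38.0 points and power 73.6%.

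| Share of loss that is early | Control | Icon | Difference (points) | Power |
|---|---|---|---|---|
| All | 0.8×0.62 = 0.496 | 0.8×0.24 = 0.192 | 30.4 | 52.4% |
| Half | 0.496 + 0.1×0.53 = 0.549 | 0.192 + 0.1×0.16 = 0.208 | 34.1 | 63.2% |
| None | 0.496 + 0.2×0.53 = 0.602 | 0.192 + 0.2×0.16 = 0.224 | 37.8 | 73.2% |

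The last row depends on most progression being visible by month 12. If only half of it is (31% and 12%), all-late loss gives (0.496 + 0.062) − (0.192 + 0.024) = 34.2 points.

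**Unequal early loss, true 38 points.** Icon 15%/control 25%: 0.465 − 0.204 = 26.1 points. Icon 25%/control 15%: 0.527 − 0.180 = 34.7. Icon 30%/control 10%: 0.558 − 0.168 = 39.0.

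**No true effect** (both arms 62% at 24 months, 53% at 12). With no loss the rejection rate is 2.8%.
- Icon 25%/control 15%, all early: 0.527 − 0.465 = 6.2 false points, 5.0% rejection.
- Icon 30%/control 10%, all early: 0.558 − 0.434 = 12.4 points, 10.5%. Half early: 7.1 points, 5.4%. None early: 1.8 points, 3.1%.

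**External treatment.** Each truly progressed lesion kept at an earlier unprogressed score lowers its arm by 1/25 = 4 points. As an illustration, 6/25 vs 15/25 gives p = 0.021. If two progressed control lesions keep an earlier score, 6/25 vs 13/25 gives p = 0.079.

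**Why plain complete cases would be worse.** Children exit at progression under section 9.5. If every 12-month progressor exits and a 24-month reading is required, the rates become (0.62−0.53)/(1−0.53) = 19.1% and (0.24−0.16)/(1−0.16) = 9.5%, a difference of 9.6 points.

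**What bounds would show.** With 20% missing per arm and observed rates of 62% and 24%, counting only the missing control lesions as progressed gives 0.696 − 0.192 = 50.4 points. Counting only the missing Icon lesions gives 0.496 − 0.392 = 10.4.

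**The case against.** Several points on the other side stand.

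The plan nowhere says that an early loss is scored as not progressed, or that baseline is an observation to be carried. A reader might take that as the protocol's wording, but it follows only from combining section 11.4.4 with the visit schedule. Progression can be noted at any point, so an interim reading is possible, and a D-category reading at a section 9.5 exit would itself be carried forward.

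A reader might infer that the rule generally inflates false positives for Icon. The figures do not support that: equal loss is conservative for the SAP's test, 25%/15% early loss only reaches the nominal 5%, and clear inflation needs something like 30%/10%. Section 9.3 allocates lesions, up to two per child are allowed, and most dropout rows act on the child. A child with a lesion in each arm removes one from both, which limits imbalance. The share of such children is not stated.

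It is also tempting to say that withdrawal for imaging distress will be heavier on Icon, because after infiltration "a post SFE laser optical device will be performed". Both arms have these examinations and no frequency is given, so this is only a possible route. Nor does the step from 42 to 50 lesions show that the SAP meant to leave dropouts out.

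On the remedy, keeping month-12 progressors while dropping lesions read as unprogressed at month 12 makes retention depend on outcome. With 20% all-late loss at the assumed rates, control is 0.602/(0.602 + 0.8×0.38) = 66.4% and Icon 0.224/(0.224 + 0.8×0.76) = 26.9%, or 39.5 points, further from 38 than the 37.8 under carry-forward. With no true effect and 30%/10% late loss, its bias is 4.9 points (against Icon), compared with 1.8.

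Finally, the filling category belongs to a secondary scale, external treatment need not be a filling, and a lesion already read as progressed keeps that score. So the external-dentist row does not contradict the primary outcome directly.

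**Conclusion.** The concern holds, as an implication of a stated rule. For lesions lost before month 12 without an interim reading, carry-forward gives a wrong primary estimate even under completely random loss, and nothing in the SAP replaces or tests it. At equal 20% loss the cost ranges from almost nothing (37.8 points) to 7.6 points (30.4 in place of 38), depending on timing. Power falls from 73.6% to 52.4% in the worst of these cases.

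These sizes rest on rates from permanent teeth, independent lesions, and assumed timing and balance of loss. Two stronger conclusions are not supported: that late loss is harmless in general (34.2 points if half of progression comes after month 12), and that a false positive for Icon is likely. This should be fixed, but the design can stand.

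**What to change.** 1. State in section 11.4.4 and the SAP that a baseline reading is never carried forward as the 24-month outcome, so a lesion with no post-baseline reading is missing. A lesion read as progressed at any visit stays progressed.
2. For a lesion read as unprogressed at month 12 and then lost, pre-specify one primary handling: carry the month-12 reading, treat as missing, or impute within arm from that reading. Report the other two as sensitivity analyses. Apply the same to the unprogressed second lesion of a child who exits under section 9.5.
3. Report analyses with all missing lesions progressed, all not progressed, and both opposite extremes. Tabulate losses by arm and by time (before or after month 12).
4. Record what any outside treatment was. For outcome scoring only, analyse an outside-filled lesion both as progressed and as missing.
5. Reconcile section 11.4.4, Table 14.1.2 and the SAP so that one scoring rule covers children who cannot be contacted, who withdraw, or who are withdrawn for distress during SFE imaging.

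The cost is wording in both documents, one case report form item and a short set of extra analyses. Somewhat fewer lesions enter the primary test. At exactly 20 per arm its power is 57.2% at the assumed rates, below the 73.6% with no loss but above the 52.4% under carry-forward when all loss is early.
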